### **13.16 Stopping Rules**

The Plexxikon Medical Monitor will monitor safety data throughout the course of the study. The Medical Monitor will review SAEs within timeframes mandated by company procedures and will review trends, laboratory analytes, and adverse events at periodic intervals and provide for interim safety analyses if appropriate. Safety data across all study patients will be reviewed at planned bimonthly teleconferences with all participating sites.

For Phase 1 dose escalation, a dose level will be considered unacceptable if 2 or more patients of the 6 eligible patients experience a DLT (see below). Should all 7 patients in the Cohort be analyzable for adverse events, only the first 6 will be considered in the determination of DLTs. A patient who misses more than 7 days of PLX3397 administration during the 7-week dosing period of Cycle 1 (4 weeks) and Cycle 2 (3 weeks) for reasons other than having had a DLT will be replaced. If 2 or more patients in a Cohort experience a DLT, no patients in the Cohort will be replaced.

If 2 or more of the first 6 patients in Cohort -2 (400 mg/day of PLX3397) experience a protocol-defined DLT, the combination will be considered too toxic and the study will be discontinued.

After approximately 50% of the planned Phase 2 patients have been completed their concurrent radiation therapy, an overall interim safety summary will be reviewed by the Medical Monitor and principal investigators to ensure that the potential clinical benefit outweighs the observed clinical risk to date. If the safety observations do not warrant continued enrollment, the study will be discontinued.

## **14.0 STUDY DRUG**

### **14.1 Study Drug Administration**

PLX3397 will be dosed orally using a capsule formulation (200 mg per capsule), twice daily in the fasting state with 240 mL (8 oz) of room-temperature water. The PLX3397 daily dose should be divided and administered twice daily approximately 12 hours apart. When the dose cannot be evenly divided, the higher of the two doses should be administered in the morning. For example, the PLX3397 1000 mg daily dose should be divided 600/400 AM/PM. For each dose, the patient should fast at least 1 hour before and 1 hour after administration. Patients will be permitted to eat a low-fat snack (e.g., crackers, toast, tea) during the fasting period if needed.

Temozolomide will be administered once daily, either in the morning or evening, also in the fasting, as noted in Section 16, either before or after PLX3397.

Study drug should be taken at approximately the same times of day, approximately 12 hours apart. On PK collection days, the morning dose of PLX3397 will be given at the clinical site; patients should be instructed NOT to take the study drug at home the morning of the clinic visit. The time of dosing will be recorded; patients will then take the evening dose at home. Between clinic visits, patients will take the study drug at home and record dosing information on the dosing diary. Missed doses (generally outside of a + 2 hour dosing window) should be skipped and not administered as a double dose at the next administration. Patients who vomit their dose should be instructed to NOT to make up that dose.

#### **14.2 Packaging and Labeling**

PLX3397-HCl capsules (200 mg strength of the active free base of PLX3397) are manufactured, packaged, and labeled according to GMP and GCP at the following address:

Catalent Pharma Solutions  
[name]  
[name]

#### **14.3 Storage and Stability**

PLX3397-HCl capsules will be stored at the clinical site, as indicated on the study drug label, i.e., room temperature (15-30°C).

Patients will be requested to store the study drug at the recommended storage conditions noted on the label, out of the reach of children or other cohabitants.

#### **14.4 Study drug Accountability, Reconciliation, and Return**

The investigator is accountable for all study drug supplied by the Sponsor. The designated copies of the completed dispensing and inventory record will be returned to the Sponsor after the Sponsor has performed accountability procedures. Returned and unused study drug should be destroyed and documented at the investigative site in accordance with GCP, after the study monitor has performed drug accountability.

#### **14.5 Study Drug Compliance**

At each clinic visit, patients will be questioned about their compliance with study drug administration, and their dosing diary should be reviewed.

### **15.0 RADIATION THERAPY**

#### **15.1 Dose Specifications and Schedule**

Intensity Modulated RT (IMRT) is allowed, but the modality chosen at registration must be used for the entire course of treatment. Proton beam therapy is not allowed. For both IMRT and 3D-CRT plans, one treatment of 2 Gy will be given daily 5 days per week for a total of 60 Gy over

approximately 6 weeks. All portals shall be treated during each treatment session, for each course/sub-course of therapy, i.e. for the initial and boost phases. Doses are specified such that at least 95% of the Planning Target Volume (PTV) shall receive 100% of the prescribed dose; Dose Volume Histograms (DVHs) are necessary to make this selection.

## **15.2 Technical Factors**

Treatment shall be delivered with megavoltage machines with a minimum energy of 6 MV photons. Selection of the appropriate photon energy/energies should be based on optimizing the radiation dose distribution within the target volume and minimizing dose to non-target normal tissue. Source skin distance for SSD techniques or source axis distance for SAD techniques must be at least 80 cm. Treatment with electrons or brachytherapy is not permissible.

## **15.3 Localization, Simulation, and Immobilization**

The patient shall be treated in the supine or other appropriate position for the location of the lesion. A head-holding device to ensure adequate immobilization during therapy and ensure reproducibility is strongly recommended. Simulation may include a dedicated radiotherapy simulator or a virtual simulation using a treatment planning CT. Fusion with MR images is strongly recommended, whenever feasible.

For patients accrued to the protocol, treatment verification and documentation should be carried out, at least for the first treatment fraction, and more frequently, based on institutional policy; weekly verification is common. We suggest orthogonal images for documenting isocenter setup accuracy for the first fraction. These orthogonal images can be obtained with film or EPID. Other imaging techniques are possible, for example, the BrainLab ExacTrac system that uses two orthogonal imaging panels irradiated with KV x-rays. Another example is the volume images obtained with cone-beam CT, or helical tomotherapy or any other CT capability that is integrated with the treatment unit. For units with built-in or “on-rail” MR capabilities, if the weekly imaging is performed with MR images, these must be fused with the baseline planning CT for purposes of verification.

## **15.4 Treatment Planning/Target Volumes**

Treatment plans may include opposed lateral fields, a wedge pair of fields, rotation, or multiple field techniques. Intensity-modulated inverse-planned approaches are permitted. Any of the methods of IMRT (including tomotherapy and volumetric arc-modulated techniques) may be used, subject to protocol localization and dosimetry constraints. CT-based treatment planning is necessary to assure accuracy in the selection of field arrangements. MRI-fusion for accurate target delineation is strongly recommended.

### **15.4.1 Initial Target Volume**

Target volumes will be based upon postoperative-enhanced MRI. Preoperative imaging may be used for correlation and improved identification as clinically necessary and relevant. Two

planning target volumes (PTV) will be defined, as outlined below. The initial gross tumor volume (GTV1) will be defined by either the T2 or the FLAIR abnormality on the post-operative MRI scan. In addition to the T2 and FLAIR volume, GTV1 must also include all postoperative MRI enhancement, and the surgical cavity. The initial clinical target volume (CTV1) will be the GTV plus a margin of 2 cm. If no surrounding edema is present, or the GTV1 volume is identical to the GTV2 volume, the initial planning target volume (PTV1) should include the contrast-enhancing lesion (and should include the surgical resection cavity) plus a 2.5-cm margin. The CTV1 margin may be reduced to as little as 0.5 cm around natural barriers to tumor growth such as the skull, ventricles, falx, etc, and also to allow sparing of the optic nerve/chiasm, or other critical structures, if necessary. The initial planning target volume (PTV1) is an additional margin of 3 to 5 mm, depending upon localization method and reproducibility, at each center. PTV margins account for variations in set-up and reproducibility. Reducing PTV margins to modify organ at risk (OAR) dose(s) is not generally permissible. However, OAR must be defined, along with a planning risk volume (PRV) for each OAR. Each PRV will be its OAR plus 3 mm. In the event that an OAR is in immediate proximity to a PTV such that dose to the OAR cannot be constrained within protocol limits, a second PTV (PTVoverlap), defined as the overlap between the PTV1 and the particular PRV of concern, may be created. Dose to the PTVoverlap must be as close as permissible to 46 Gy while not exceeding the OAR dose limit.

#### **15.4.2 Boost Target Volume**

The boost gross tumor volume (GTV2) will be defined by the contrast-enhanced T1 abnormality on the post-operative MRI scan. This must also include the surgical cavity. The boost clinical target volume (CTV2) will be the GTV plus a margin of 2 cm. The CTV2 margin may be reduced to as little as 0.5 cm around natural barriers to tumor growth such as the skull, ventricles, falx, etc, and also to allow sparing of the optic nerve/chiasm, or other critical structures, if necessary. The boost planning target volume (PTV2) is an additional margin of 3 to 5 mm, depending upon localization method and reproducibility, at each center. PTV margins account for variations in set-up and reproducibility. Reducing PTV margins to modify organ at risk (OAR) dose(s) is not generally permissible. However, OAR must be defined, along with a planning risk volume (PRV) for each OAR. Each PRV will be its OAR plus 3 mm. In the event that an OAR is in immediate proximity to a PTV such that dose to the OAR cannot be constrained within protocol limits, a second PTV (PTVoverlap), defined as the overlap between the PTV2 and the particular PRV of concern, may be created (the overlap is the intersection between the PTV1 and the PRV). Dose to the PTVoverlap must be as close as permissible to 14 Gy while not exceeding the OAR dose limit.

#### **15.4.3 Dose Guidelines**

The initial target volume will be treated to 46 Gy in 23 fractions. After 46 Gy, the conedown or boost volume will be treated to a total of 60 Gy, with seven additional fractions of 2 Gy each (14 Gy boost dose).

Isodose distributions for the initial target volume (PTV1) and the conedown target volume (PTV2) are required on all patients. A composite plan is required showing the respective target volumes. The inhomogeneity within the target volume shall be kept to  $\pm 10\%$  of the prescribed dose.

The minimum dose to the target volume should be kept within 10% of the prescribed. Doses are specified such that at least 95% of the PTV shall receive 100% of the prescribed dose; DVHs are necessary to make this selection.

#### 15.4.4 Dose Limitations and Critical Structures

In addition to the above defined GTVs, CTVs and PTVs the lenses of both eyes, both retinae, both optic nerves, the optic chiasm, and the brainstem must be defined. The maximum point (defined as a volume greater than 0.03 cc) doses permissible to the structures are listed in the table below.

**Table 6: Maximum Doses Permissible for Critical Structures**

Critical Structure	Maximum Dose
Lenses	8 Gy
Retinae	50 Gy
Optic Nerves	56 Gy
Optic Chiasm	56 Gy
Brainstem	61 Gy

#### 15.5 Compliance Criteria

For all patients, as mentioned above, two PTV prescriptions, PTV1 and PTV2 will be used and the prescription isodose (46 Gy for PTV1 and 14 Gy for PTV2) must cover >95% of the PTV volume; therefore, the total dose in the PTV2 volume will be 60 Gy. The minimum acceptable dose within PTV1 will be 41.4 Gy (90% of 46 Gy), and in the PTV2 volume, it will be 54 Gy (90% of 60 Gy). This minimum dose must cover 100% of the PTV. If the minimum dose falls below these parameters, an unacceptable deviation will be assigned. The maximum dose for the PTV2 should not exceed 66 Gy (110% of 46 Gy). If the maximum doses exceed these parameters, an unacceptable deviation will be assigned.

Up to 5 days of treatment interruption are permitted for any reason. Interruptions of 6 to 7 treatment days will be considered an acceptable protocol deviation. For interruptions of 8 days or greater, continuation of patients in the study should be discussed with the medical monitor.

## **15.6 Radiation Therapy Adverse Events**

### **15.6.1 Acute**

Expected acute radiation-induced toxicities include hair loss, fatigue, and erythema or soreness of the scalp. Potential acute toxicities include nausea and vomiting as well as temporary aggravation of brain tumor symptoms such as headaches, seizures, and weakness. Reactions in the ear canals and on the ear should be observed and treated symptomatically; these reactions could result in short-term hearing impairment. Dry mouth or altered taste have been occasionally reported.

### **15.6.2 Early Delayed**

Possible early delayed radiation effects include lethargy and transient worsening of existing neurological deficits occurring 1-3 months after radiotherapy treatment.

### **15.6.3 Late Delayed**

Possible late delayed effects of radiotherapy include radiation necrosis, endocrine dysfunction, and radiation-induced neoplasms. In addition, neurocognitive deficits, which could lead to mental slowing and behavioral change, are possible. Permanent hearing impairment and visual damage are rare. Cataracts can be encountered.

## **16.0 TEMOZOLOMIDE THERAPY**

### **16.1 Temozolomide During Concomitant Radiation Therapy**

Temozolomide will be administered continuously from day 1 of radiotherapy to the last day of radiotherapy at a daily oral dose of  $75 \text{ mg/m}^2$  for a maximum of 49 days. The drug will be administered orally 1 hour before each session of radiotherapy during weekdays (Monday through Friday). During weekends without radiotherapy (Saturday and Sunday), the drug will be taken in the morning.

The dose will be determined using actual body surface area (BSA) as calculated in square meters at the beginning of the concomitant treatment. The BSA will be calculated from the height obtained at the pretreatment visit and the weight obtained at the visit immediately before the first day of treatment. Capsules of temozolomide are available in 5, 20, 100, 140, 180, and 250 mg. The daily dose will be rounded to the nearest 5 mg. If the investigator does not want to prescribe the temozolomide 5 mg unit strength, he/she should round off the dose to the closest 10 mg. For example, for a  $1.7 \text{ m}^2$  subject, the  $75 \text{ mg/m}^2$  dose would be 127.5 mg and the dose would be rounded off to 120 mg. For the same subject, the  $150 \text{ mg/m}^2$  dose would be 255 mg and the dose would be rounded off to 260 mg. The exact dose administered should be recorded in the CRF. Each daily dose should be given with the least number of capsules.

Patients will be instructed to swallow the capsules whole, in rapid succession, without chewing them. If vomiting occurs during the course of treatment, no re-dosing of the patient is allowed

before the next scheduled dose. The capsules should be taken on an empty stomach, therefore a minimum of 2 hours after eating and with no food consumption for at least 1 hour after temozolomide administration. Although, nightly administration just before bedtime has been reported to improve tolerance, the low daily dose administered during radiation is very well tolerated and administration in the morning before radiation dosing is required for this protocol. Administration of the higher dosing regimen during the adjuvant phase of the protocol should be performed using the nightly administration.

Antiemetic prophylaxis is usually not required for the continuous daily dosing schedule (during radiation). However, prophylaxis with a 5-HT3 antagonist is recommended prior to administration of the first few temozolomide doses and should be administered orally 30 to 60 minutes before temozolomide treatment. Most patients report optimal nausea control with the use of a 5-HT3 antagonist. Routine use of antiemetics is recommended during the adjuvant phase of treatment. Additionally, pneumocystis carinii prophylaxis is at the discretion of the Investigator during the radiation phase.

During the 4-week break after completion of radiotherapy, neither temozolomide nor study drug will be administered.

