**TABLE 4: Dosing Modification Table**

**TABLE 5: Daily Dose Calculations by Body Surface Area (BSA)**

Total BSA (m  )	75 mg/m  (mg daily)	150 mg/m  (mg daily)	200 mg/m  (mg daily)
1.0	75	150	200
1.1	82.5	165	220
1.2	90	180	240
1.3	97.5	195	260
1.4	105	210	280
1.5	112.5	225	300
1.6	120	240	320
1.7	127.5	255	340
1.8	135	270	360
1.9	142.5	285	380
2.0	150	300	400
2.1	157.5	315	420
2.2	165	330	440
2.3	172.5	345	460
2.4	180	360	480
2.5	187.5	375	500

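### The worked example for temozolomide rounding (127.5 mg to 120 mg) does not follow its own 10 mg rule, the rule can give a dose that cannot be dispensed, and ties are left open

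*Combined protocol and SAP*

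**What the plan says.** Section 16.1 (temozolomide with radiotherapy, 75 mg/m² daily) gives two rounding rules. The default is "The daily dose will be rounded to the nearest 5 mg". If the investigator does not want to prescribe the 5 mg strength, "he/she should round off the dose to the closest 10 mg". Two worked examples follow for a 1.7 m² patient. At 75 mg/m², the calculated dose is 127.5 mg and "the dose would be rounded off to 120 mg". At 150 mg/m², the "dose would be 255 mg and the dose would be rounded off to 260 mg". The strengths are listed in the same paragraph: "Capsules of temozolomide are available in 5, 20, 100, 140, 180, and 250 mg".

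Section 16.2 (adjuvant temozolomide, 150 to 200 mg/m²) repeats both rules and both examples. Both sections also ask that each daily dose use as few capsules as possible and that the exact dose given be recorded in the CRF.

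Attachment 4, the prescribing information to which section 16.3 refers, lists calculated doses by body surface area in Table 5 and suggested capsule combinations in Table 6. Table 6 makes up 127.5 mg from one 100 mg, one 20 mg and one 5 mg capsule.

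**The concern.** The 120 mg example comes directly after the 10 mg rule and is there to show how it works, but 127.5 is closer to 130 than to 120. A pharmacist who applies the sentence and one who copies the example reach different doses for the same patient. This is an operating instruction for a drug taken daily through about six weeks of radiotherapy, with a maximum of 49 days. Two sites could therefore differ while each follows the protocol, and a monitor could not say which dose is the deviation. The trial is uncontrolled and adds PLX3397 to standard temozolomide and radiotherapy, so avoidable variation in the backbone is worth removing.

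**Working it through.** **Inputs.** Dose 75 mg/m² and both rounding rules: section 16.1. Body surface area 1.7 m²: the worked example. Capsules 5, 20, 100, 140, 180 and 250 mg: section 16.1. Calculated doses: Attachment 4 Table 5, whose row for 1.7 m² reads "1.7 127.5 255 340" (body surface area, then mg daily at 75, 150 and 200 mg/m²).

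**1. The plan's own figures.** 75 × 1.7 = 127.5 mg and 150 × 1.7 = 255 mg. Both calculated doses are correct; only the rounding is in question.

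**2. The 10 mg rule on 127.5 mg.** Distance to 120 = 7.5; distance to 130 = 2.5. The rule gives 130 mg, so the stated 120 mg is not reproduced.

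**3. The 5 mg rule on 127.5 mg.** Distance to 125 = 2.5; distance to 130 = 2.5. This is an exact tie, and 120 mg is not a candidate. Neither written rule gives 120 mg.

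**4. Can 130 mg be dispensed without 5 mg capsules?** The remaining strengths are 20, 100, 140, 180 and 250 mg. All but 250 are multiples of 20, and 250 already exceeds 130. The nearest doses that can be made are 120 (100 + 20) and 140. So 130 mg cannot be dispensed under the condition that triggers the rule. With 5 mg capsules it can (100 + 20 + 5 + 5).

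**5. How often this happens at 75 mg/m².** The 10 mg rule applied to all 16 rows of Table 5, without 5 mg capsules:

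| Result | Body surface area (m²): calculated → rounded (mg) | Rows |
|---|---|---|
| Can be dispensed | 1.1: 82.5→80; 1.3: 97.5→100; 1.6: 120→120; 1.9: 142.5→140; 2.1: 157.5→160; 2.4: 180→180 | 6 |
| Cannot be dispensed | 1.2: 90→90; 1.5: 112.5→110; 1.7: 127.5→130; 2.0: 150→150; 2.3: 172.5→170; 2.5: 187.5→190 | 6 |
| Tie, no direction given | 1.0: 75; 1.4: 105; 1.8: 135; 2.2: 165 | 4 |

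**6. Ties elsewhere.** Under the 10 mg rule, 255 mg is 5 from 250 and 5 from 260, so the second example is compatible with the rule but not determined by it. Under the 5 mg rule, the eight Table 5 doses at 75 mg/m² that end in 2.5 or 7.5 are exact ties. Table 6 resolves them in both directions: for example, 82.5 is filled as 80 and 127.5 as 100 + 20 + 5 = 125, but 97.5 as 100 and 157.5 as 160. The request for fewest capsules is not a tie-break either: 250 mg needs one capsule and 260 mg needs three, yet the example takes 260.

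**7. Size for a 1.7 m² patient.**

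| Daily dose | Source | Relative to 127.5 mg | mg/m² |
|---|---|---|---|
| 120 mg | Worked example | 120/127.5 - 1 = -5.9% | 70.6 |
| 125 mg | 5 mg rule with the tie taken down; Table 6 | 125/127.5 - 1 = -2.0% | 73.5 |
| 130 mg | 5 mg rule with the tie taken up; 10 mg rule read literally | 130/127.5 - 1 = +2.0% | 76.5 |

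The widest gap is 10 mg a day: 10 × 42 = 420 mg over 42 days, or 10 × 49 = 490 mg over 49 days.

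**The case against.** The strongest defence is that 120 mg is the closest dose that can be dispensed without 5 mg capsules, so the example is practical and the rule is only loosely worded. Both examples are also the nearest multiple of 20 mg (120 is 7.5 from 127.5 against 12.5 for 140; 260 is 5 from 255 against 15 for 240). This probably explains the figure, but it does not remove the defect. The text states a 10 mg rule, not a nearest-dispensable rule or a 20 mg rule, and a reader cannot recover the intention from it.

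A second defence is that Attachment 4 Table 6 does not contradict the example. That stands. The example belongs to the branch without 5 mg capsules, whereas Table 6 uses one to reach 125 mg. It is therefore consistent with the default 5 mg rule with the tie taken down. It also offers suggested combinations within an attached label. A reader might infer a three-way contradiction, but the only firm one is between example and rule. What Table 6 adds is a second tie handled without a stated convention.

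Two smaller points also stand. The 75 mg/m² example in section 16.2 is repeated text that does not govern the adjuvant dose, although the 255 mg example there does bear on it. And the choice whether to prescribe 5 mg capsules is deliberately left to the investigator, so some difference between patients is intended.

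**Conclusion.** The point holds as an inconsistency in an operating instruction. The example departs from the rule it illustrates, in both sections. The rule yields a dose that cannot be dispensed under its own condition in 6 of 16 body-surface-area rows at 75 mg/m². Ties are undecided under both rules. For a 1.7 m² patient the documents can support 120, 125 or 130 mg a day, from 5.9% below to 2.0% above the calculated dose. The count of 6 assumes only the listed capsule strengths, whole capsules and no 5 mg capsule; it is a count of table rows, not an estimate of the share of patients.

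Two stronger readings are tempting and not supported. One is that sites will in fact give three different doses: the documents show only that they can, and 130 mg is reachable only where 5 mg capsules are used. The other is that the comparison with the historical control is compromised: nothing in the documents links a rounding difference of this size to progression-free survival, and sample size, power and the primary analysis do not depend on it. The dose actually given is to be recorded in the CRF, so any variation should be visible. This is a minor point, worth correcting because correction is cheap.

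**What to change.** In sections 16.1 and 16.2, reconcile four things so that they agree: the rounding rule when the 5 mg strength is not used, its worked example, the capsule strengths available in that case, and the direction in which ties are resolved under each rule. State whether Attachment 4 Table 6 governs, or is only a guide, when 5 mg capsules are used. In section 16.2, check whether the 75 mg/m² example belongs there at all. The investigator's choice about the 5 mg strength need not be removed; it is enough that, once the choice is made, one calculated dose leads to one administered dose. Which dose that should be is for the sponsor and investigators to settle; none is proposed here.

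The cost is a wording change in two sections and a short clarification to sites. No procedure, sample size or analysis changes.
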